#### Lymph Nodes lesions:

F-DCFPyL positive lymph nodes will be considered. Lymph nodes will be assessed by change in size.

#### True positive:

1) For patients undergoing systemic treatment (alone or in combination with targeted treatment): If on post-treatment follow-up imaging within 3-12 months, lymph nodes seen

on CT or MRI decrease by more than 30% in short axis diameter and PSA declines by more than 50%.

- If PSA increases by more than 50% on systemic therapy, then a increase in the size of lesion by more than 20% will be considered a true positive lesion.
- 2) In subjects with localized suspected lymph node(s) receiving targeted treatment without concomitant systemic treatment there are two ways to meet true positive disease:
  - If the subject shows a decrease of PSA by greater than 50% after targeted treatment and the lymph node does not enlarge (change in size less than 20% or less than 3 mm increase in short axis diameter) [OR]
  - If on post-treatment follow-up imaging within 3-12 months, lymph nodes seen on CT or MRI decrease by more than 30% in short axis diameter (with a minimum of 3 mm in change in size)
- 3) For untreated patients: If on follow-up imaging within 3-12 months, lymph nodes seen on CT or MRI increase by more than 20% in short axis diameter (with a minimum of 3 mm in change in size).

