#### False positive:

- 1) For patients undergoing systemic treatment (alone or in combination with targeted treatment): If on post-treatment follow-up imaging within 3-12 months, lymph nodes seen on CT or MRI increase by more than 20% in short axis diameter and PSA decreases by more than 50%.
- 2) In subjects with localized suspected lymph node(s) receiving targeted treatment without concomitant systemic treatment there are two ways to meet false positive disease:
  - If the subject does not demonstrate a decrease of PSA by greater than 50% after targeted treatment [OR]
  - If on post-treatment follow-up imaging within 3-12 months, lymph nodes seen on CT or MRI increase by more than 20% in short axis diameter (with a minimum of 3 mm in change in size)
- 3) For untreated patients: If on follow-up imaging within 3-12 months, lymph nodes seen on CT or MRI decrease by more than 30% in short axis diameter (with a minimum of 3 mm in change in size).

If all regions in a patient/region do not meet criteria for either True positive or False positive disease, then the patient/region will be considered unevaluable for primary endpoint.

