#### True positive:

- For patients undergoing systemic treatment (alone or in combination with targeted treatment): If on post-treatment follow-up imaging within 3-12 months, lesions seen on CT or MRI decrease by more than 30% in long axis diameter
- 2) In subjects with localized suspected lesions(s) receiving targeted treatment without concomitant systemic treatment there are two ways to meet true positive disease:
  - If the subject demonstrates a decrease of PSA by greater than 50% after targeted treatment [OR]
  - If on post-treatment follow-up imaging within 3-12 months, lesions seen on CT or MRI decrease by more than 30% in long axis diameter (with a minimum of 3 mm in change in size)
- 3) For untreated patients: If on follow-up imaging within 3-12 months, lesions seen on CT or MRI increase by more than 20% in long axis diameter (with a minimum of 3 mm in change in size).

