#### False positive:

1) For patients undergoing systemic treatment (alone or in combination with targeted treatment): If on post-treatment follow-up imaging within 3-12 months, lesions seen on CT

- or MRI increase by more than 20% in long axis diameter and PSA decreases by more than 50%.
- 2) In subjects with localized suspected lesions(s) receiving targeted treatment without concomitant systemic treatment there are two ways to meet false positive disease:
  - If the subject does not demonstrate a decrease of PSA by greater than 50% after targeted treatment [OR]
  - If on post-treatment follow-up imaging within 3-12 months, lesions seen on CT or MRI increase by more than 20% in long axis diameter (with a minimum of 3 mm in change in size)
- 3) For untreated patients: If on follow-up imaging within 3-12 months, lesions seen on CT or MRI decrease by more than 30% in long axis diameter (with a minimum of 3 mm in change in size).

If the lesion does not meet criteria for either True positive or False positive disease, then the lesion will be considered inevaluable for primary endpoint.

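### The prostate true-positive rule under systemic treatment has neither a PSA condition nor a 3 mm minimum, and no systemic-treatment size rule carries the 3 mm minimum used in the other treatment groups

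*Combined protocol and SAP*

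**What the plan says.** The rules are in section 1.1.8.4 (Measurements), part 2A (follow-up imaging), separately for nodes, viscera, bone and prostate. Within the three soft-tissue lesion types they are split by treatment received: systemic (with or without targeted), targeted only, and none.

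**Systemic treatment, nodes.** True positive: a "decrease by more than 30% in short axis diameter and PSA declines by more than 50" per cent. If PSA instead rises by more than 50%, "then a increase in the size of lesion by more than 20% will be considered a true positive lesion". False positive: "lymph nodes seen on CT or MRI increase by more than 20% in short axis diameter and PSA decreases by more than 50" per cent. The visceral rules have the same structure on the long axis.

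**Systemic treatment, prostate.** True positive: "lesions seen on CT or MRI decrease by more than 30% in long axis diameter", with nothing further. False positive: "increase by more than 20% in long axis diameter and PSA decreases by more than 50" per cent. There is no rising-PSA branch.

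**Targeted only and untreated.** Each size-change rule adds a 3 mm minimum. Nodal examples are "decrease by more than 30% in short axis diameter (with a minimum of 3 mm in change in size" for a targeted-only true positive and "increase by more than 20% in short axis diameter (with a minimum of 3 mm in change in size" for an untreated true positive. The nodal targeted-only rule based on PSA also uses 3 mm: with a PSA fall above 50%, the node counts as not enlarged if it changed by less than 20% or grew by less than 3 mm.

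The classifications feed the per-patient and per-region PPV (sections 1.1.3.3 and 1.1.9.5). RECIST 1.1 and PCWG3 are cited only for progression-free survival (section 1.1.9.4), so they supply no minimum here.

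**The concern.** There are two gaps. The narrower and clearer one is the prostate true-positive rule under systemic treatment. It is the only size-change rule in the set with neither a PSA condition nor a minimum change in millimetres. Its false-positive counterpart and the nodal and visceral true-positive rules all require a PSA fall above 50%.

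The wider gap is that the 3 mm minimum is absent from all systemic-treatment size rules: true-positive and false-positive rule 1 for nodes, viscera and prostate, and the rising-PSA branches for nodes and viscera. PSA is a patient-level value. It limits which patients reach the size criterion, but does not show whether a given lesion really changed. Nodal and visceral rule 1 use the same PSA condition for true and false positives. Once PSA has fallen by more than 50%, size alone separates true positive, false positive and unevaluable.

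Small lesions could therefore be classified by measurement error, and identical measurements can give opposite verdicts depending on treatment group. The quantity at stake is PPV, a secondary endpoint. The text calls unclassified lesions unevaluable for the primary endpoint, but the primary endpoint is management change, which these rules do not touch.

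**Working it through.** **Step 1. Rules side by side** (size-change rules only)

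| Lesion, rule | Systemic: PSA condition | Systemic: 3 mm | Targeted-only and untreated: 3 mm |
|---|---|---|---|
| Node, true positive | fall >50% (or rise >50% with growth) | no | yes |
| Node, false positive | fall >50% | no | yes |
| Viscera, true positive | fall >50% (or rise >50% with growth) | no | yes |
| Viscera, false positive | fall >50% | no | yes |
| Prostate, true positive | **none** | no | yes |
| Prostate, false positive | fall >50% | no | yes |

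Bone rules do not use size and are unaffected.

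**Step 2. One node, two verdicts.** Take a 6 mm node that grows 1.3 mm in a patient whose PSA falls by more than 50%. The growth is 1.3/6 = 21.7%.
- Targeted treatment only: growth is below 3 mm, so the node has not enlarged, and with the PSA fall it is a true positive. It misses the false-positive size rule, which needs 3 mm.
- Systemic treatment, alone or with targeted: growth exceeds 20% and PSA has fallen by more than 50%, so it is a false positive.

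**Step 3. Where the percentages fall below 3 mm.** 3/0.30 = 10 mm and 3/0.20 = 15 mm. A 30% decrease is under 3 mm for lesions below 10 mm, and a 20% increase is under 3 mm for lesions below 15 mm. At 6 mm the thresholds are 1.8 mm and 1.2 mm. At or above 10 mm (30% rule) and 15 mm (20% rule) the minimum changes nothing.

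**Step 4. Noise in a lesion that has not changed.** The documents give no measurement error. Assume normal error with SD 0.7 to 1.0 mm per reading. The SD of a difference of two readings is s = √2 × SD, that is 0.99 to 1.41 mm. For baseline diameter d:
- P(decrease beyond 30%) = Φ(−0.30d/s)
- P(increase beyond 20%) = Φ(−0.20d/s)
- With the minimum, replace 0.30d or 0.20d by the larger of that value and 3 mm.

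For d = 6 mm:

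| s (mm) | beyond −30% | beyond +20% | either one, with 3 mm |
|---|---|---|---|
| 0.50 | Φ(−3.60) = 0.02% | Φ(−2.40) = 0.8% | about 0% |
| 0.99 | Φ(−1.82) = 3.5% | Φ(−1.21) = 11.3% | Φ(−3.03) = 0.1% |
| 1.41 | Φ(−1.27) = 10.2% | Φ(−0.85) = 19.8% | Φ(−2.12) = 1.7% |
| 2.00 | Φ(−0.90) = 18.4% | Φ(−0.60) = 27.4% | Φ(−1.50) = 6.7% |

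The first and last rows show the sensitivity to the assumption. For nodes and viscera, and for the prostate false-positive rule, these are probabilities given the required PSA change. For the prostate true-positive rule they are unconditional.

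**Step 5. Direction for prostate lesions.** Noise yields a true positive with probability 3.5–10.2%. It yields a false positive with probability 11.3–19.8% multiplied by q, the share of patients with a PSA fall above 50% (taking PSA as independent of size error). The two are equal at q = 0.0345/0.1127 = 31% for s = 0.99 and q = 0.1015/0.1981 = 51% for s = 1.41. The documents do not give q.

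**The case against.** The strongest defence is that the rules follow a design: a size criterion carries either a PSA condition or the 3 mm minimum, so for nodes and viscera PSA deliberately stands in for the minimum. This does not stand. The nodal targeted-only rule uses a PSA fall and the 3 mm limit together, and the prostate systemic true-positive rule has neither.

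Other objections do stand in part:
- The noise probabilities cover the size criterion only. Except for the prostate true-positive rule, a verdict also needs the PSA change.
- They depend on an SD and a lesion size that the documents do not give. At s = 0.5 mm the effect is negligible.
- Later rules dampen the effect. Pathology outranks imaging, and an imaging true positive overrides imaging false positives at region and patient level (part 2C).
- Part 2C lets investigators depart from the criteria and record it. That permits case-by-case correction but supplies no limit.

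A reader might infer that prostate true positives are easier to reach than false positives, so PPV is inflated. The documents do not support this. The missing PSA condition loosens the true-positive rule, but 30% is harder for noise to cross than 20%, and the balance turns on an unknown share of PSA falls. For nodes and viscera, noise after a PSA fall favours false positive, while growth by noise after a PSA rise gives true positive.

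**Conclusion.** The inconsistency is in the text and needs no assumption: one prostate rule lacks both safeguards, the 3 mm minimum is missing from every systemic-treatment size rule, and the same node can be classified in opposite ways by treatment group. The numerical size is conditional. For an unchanged 6 mm lesion with 0.7 to 1.0 mm SD per reading, noise meets the size criterion in 3.5–10% (−30%) or 11–20% (+20%), against 0.1–1.7% with the minimum. No lesion-size distribution is given, so the share of lesions affected and the effect on PPV cannot be computed, and no net direction is established. This is a minor point on a secondary endpoint. It would be too strong to conclude that unchanged nodes are generally labelled by measurement error.

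**What to change.** 1. Add the 3 mm minimum, worded as in the targeted-only and untreated rules, to the systemic-treatment true-positive and false-positive size rules for nodes, viscera and prostate. Include the rising-PSA branches for nodes and viscera.
2. Add the condition of a PSA fall above 50% to the prostate systemic true-positive rule, to match its false-positive counterpart and the nodal and visceral rule 1. Prostate has no rising-PSA branch, so say whether that is intended.
3. If either omission is deliberate, state the reason.
4. Report how many lesions, regions and patients change category, and give PPV under both the current and the revised rules as a sensitivity analysis.

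The edit is short, but it has a cost. For a 5 to 6 mm node, 3 mm is 3/5 = 60% to 3/6 = 50% of its diameter, so some small lesions become unevaluable. So do prostate lesions that shrink without the PSA fall. Unevaluable regions leave the PPV denominator, so the loss is selective. The opening abstract reports 150 patients already scanned and section 1.1.9.6 mentions an interim analysis, so lesions already adjudicated would need reclassifying. These rules classify outcomes; no patient's treatment changes.

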# **Secondary Endpoints:**

- 1. Prognostic value of the F-DCFPyL PET/CT miTNM classification (described below) for biochemical PFS, radiographic PFS and overall survival.
- 2. Positive predictive value (PPV) on a per-patient and per-region basis (Table 1) of F-DCFPyL PET for detection of tumor location confirmed by histopathology/biopsy or follow-up assessed separately for initial staging and restaging.

Region	Description
1	Prostate Bed
2	Pelvic lymph nodes
3	Extrapelvic soft tissue, lymph nodes and visceral metastases
4	Bone metastases

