#### True positive:

- 1) If there was a corresponding positive sclerotic lesion on the CT portion of the  $^{68}$ Ga- $^{18}$ F-DCFPyL PET or on a separate CT obtained  $\leq$  30 days before or after the PET/CT in the same location as the PSMA uptake.
- 2) If there is focal uptake seen in the same location as the PSMA uptake on the baseline bone scan performed within one month of F-DCFPyL PET.
- 3) If there is a lesion noted in the same location as the PSMA uptake on the initial MRI performed within one month of F-DCFPyL.

- 4) If within 12 months follow-up CT demonstrates development of sclerosis in the same location as the PSMA uptake.
- 5) If within 12 months follow-up MRI demonstrates a new bone lesion in the same location as the PSMA uptake.
- 6) If within 12 months follow-up bone scan demonstrates new focal uptake in the same location as the PSMA uptake.
- 7) In subjects with localized suspected bone lesion(s) receiving targeted treatment without concomitant systemic treatment:
  - If the subject demonstrates a decrease of PSA by greater than 50% after targeted treatment.

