# B) HISTOPATHOLOGY/BIOPSY:

Localization of lesions for histopathology/biopsy will be a classified by regions as specified in the miTNM framework. F-DCFPyL positive findings are aimed to be confirmed by histopathology (HP)/biopsy if clinically feasible. Pathology performed 60 days before the F-DCFPyL PET will be available for correlation. Histopathological procedures, biopsies and follow-up imaging will be performed as clinically indicated and as per institutional protocol.

The following elective procedures may guide the investigator:

Positive HP/Biopsy: Confirmed sites of metastatic or tumor involvement by histopathology/biopsy will be discussed with the responsible physician/surgeon.

- a) *True Positive*: lesion is positive on targeted biopsy/surgical sampling and is read as positive on F-DCFPvL PET.
- b) False Negative: lesion is positive on targeted biopsy/surgical sampling and is read as negative on F-DCFPyL PET.

Negative HP/Biopsy: Patients with suspected tumor recurrence on F-DCFPyL PET with negative histopathology/biopsy will be handled as outlined below:

- 1) Lymph nodes:
  - i) For patients undergoing nodal dissection: Patients will be rescanned with dedicated CT, MRI or a repeat F-DCFPyL PET to determine if the suspicious F-DCFPyL positive node was removed.
    - (1) If F-DCFPyL positive lymph node is still present, a repeat biopsy can be pursued if clinically feasible and applicable, or follow-up using imaging as described above will be performed.
    - (2) If the corresponding node was removed, then this will be considered a False Positive.

- ii) For patients undergoing needle biopsy: Images of the procedure will be reviewed to determine if the correct node was biopsied.
  - (1) If the correct node was biopsied, then a negative biopsy will be considered a False Positive.
  - (2) If the incorrect node was biopsied, then follow-up imaging as described above will be performed.
- 2) Bone lesions: Given the high rate of false negative biopsies for osseous metastases in patients with prostate cancer, patients with negative bone biopsies of PSMA PET positive lesions will be further evaluated:
  - a) If pathology demonstrates an alternative diagnoses that is known to be PSMA positive (eg Renal Cell Carcinoma metastases, Paget's disease), then this will be considered a False Positive.

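### On the targeted-treatment route a single patient-level PSA result classifies individual PET lesions, so per-region PPV is biased for those regions when an in-place primary is treated in the same course

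*Combined protocol and SAP*

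**What the plan says.** PPV per patient and per region is the second secondary endpoint (1.1.3.3), to be "confirmed by histopathology/biopsy or follow-up assessed separately for initial staging and restaging". Section 1.1.9.5 reports it with Wilson 95% intervals for each blinded reader. It sets no target value.

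Without pathology, section 1.1.8.4, 2) A) classifies each PET-positive lesion from follow-up. One branch covers patients given targeted treatment and no concomitant systemic treatment:

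- **Nodes, true positive:** "If the subject shows a decrease of PSA by greater than 50% after targeted treatment and the lymph node does not enlarge", where not enlarging means "change in size less than 20% or less than 3 mm increase in short axis diameter". An alternative route is shrinkage of more than 30% (at least 3 mm), with no PSA condition.
- **Visceral, bone (rule 7) and prostate lesions, true positive:** "If the subject demonstrates a decrease of PSA by greater than 50% after targeted treatment". No condition on the lesion itself is attached.
- **False positive:** "If the subject does not demonstrate a decrease of PSA by greater than 50% after targeted treatment". This stands alone for nodes, visceral and prostate lesions. For bone it applies only to curative-intent treatment.

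For nodes the branch opens with "In subjects with localized suspected lymph node(s) receiving targeted treatment without concomitant systemic treatment there are two ways to meet true positive disease". Targeted treatment is not defined further. The rules that use a measured size change look at imaging within 3-12 months; the PSA value has no window. The rules are the same for initial staging and restaging. Section C) ranks pathology above follow-up. Without pathology, it lets a true-positive lesion outweigh a false-positive one in the same region.

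**The concern.** PSA is one number per patient. It speaks to a particular lesion only if that lesion is the only PSA source that was treated. At initial staging the prostate is still in place. If it is treated in the same course as a PET-positive node or distant focus, PSA can halve because the primary was treated, whether or not the node or focus was cancer. A stable benign node then meets the node rule, and a bone focus needs nothing beyond the PSA fall. With several PET-positive regions treated, one PSA result bears on all of them.

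The protocol is stricter elsewhere. It says nodes and visceral lesions are judged by change in size, and its systemic-treatment branch for both asks for shrinkage together with a PSA decline; the targeted-only branch drops the shrinkage. For bone, false-positive rule 2 covers a focus that was adequately imaged and met no true-positive criterion. Rule 7 makes the same focus a true positive on PSA alone.

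At stake is whether the regional PPV at initial staging shows that PET located tumour or, for these regions, that treatment lowered PSA.

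**Working it through.** **The plan's own figures.** The plan gives no expected PPV and no PPV sample size. Its only power statement concerns the primary management endpoint: more than 90% for 53% against 40%, N = 400, one-sided 0.025, exact binomial. That reproduces (critical count 180, exact alpha 0.0238, power 0.9994) but has no bearing here.

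**Inputs, all assumed; the documents give none.**
- v: true share of PET-positive lesions that are cancer.
- f1, f0: probability of a PSA fall above 50% when the lesion is, or is not, cancer.
- e1 = 0.10, e0 = 0.02: probability that a malignant or benign node enlarges.
- w: share of evaluable regions classified by this route, the rest taken as correctly classified.

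**Formulas**, with every lesion not called true positive counted as false positive:
- Bone without an imaging correlate, and visceral: PPV = v·f1 + (1−v)·f0.
- Nodes, PSA route only: PPV = v·f1·(1−e1) + (1−v)·f0·(1−e0).
- Overall: w·(route PPV) + (1−w)·v.

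The bone formula returns v for every v only if f1 = 1 and f0 = 0. A treated primary pushes f0 up.

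**Case 1: PSA follows the primary, f1 = f0 = 0.95.**
- Bone: 0.95·v + 0.95·(1−v) = 0.95 for every v.
- Nodes: v = 0 gives 0.95 × 0.98 = 0.931; v = 0.5 gives 0.893; v = 1 gives 0.95 × 0.90 = 0.855.

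**Case 2: true disease keeps PSA up in some patients, f1 = 0.80, f0 = 0.95.**
- Nodes: v = 0 gives 0.931; v = 1 gives 0.80 × 0.90 = 0.720. The classified PPV moves opposite to the truth.

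**Overall PPV, nodes, case 2:**

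| True PPV | Route PPV | w = 10% | w = 25% | w = 50% |
|---|---|---|---|---|
| 0.50 | 0.826 | 0.533 | 0.581 | 0.663 |
| 0.90 | 0.741 | 0.884 | 0.860 | 0.821 |

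For example, 0.10 × 0.826 + 0.90 × 0.50 = 0.533. With case 1 inputs and true PPV 0.50, the results are 0.10 × 0.893 + 0.45 = 0.539 at 10% and 0.50 × 0.893 + 0.25 = 0.697 at 50%.

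**Adding the node shrinkage route.** A node with no PSA fall that shrinks by more than 30% meets a true-positive and a false-positive rule; the region rule favours true positive. Assume that, without a PSA fall, 50% of malignant and 5% of benign nodes shrink that far.
- Case 1: malignant 0.855 + 0.05 × 0.50 = 0.880; benign 0.931 + 0.05 × 0.05 = 0.934.
- Case 2: malignant 0.720 + 0.20 × 0.50 = 0.820; benign again 0.934. At v = 0.5 the route PPV is 0.877, and overall PPV is 0.538 at w = 10% and 0.688 at w = 50%.

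Shrinkage restores some dependence on true status, but benign nodes are still called true positive about 93% of the time.

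**The case against.** The strongest reply is that this is one branch among several. Pathology overrides it. Systemically treated nodes and visceral lesions need a size change as well as a PSA change, untreated nodal, visceral and prostate lesions need a size change, and bone has six imaging routes to true positive. Section C) also lets investigators depart from the criteria in individual patients and record it. PPV is a secondary, descriptive endpoint. All of this limits the reach of the problem. It does not repair the rule, because case-by-case discretion does not tell two investigators to label the same lesion the same way.

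Four stronger readings are tempting, and the documents do not support them.

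- *Treating the primary alone confirms nodes and bone.* This requires targeted treatment to include treatment not aimed at the lesion. The wording permits that but does not state it, and the natural reading is that the suspected lesion is treated. What stands is that the term is undefined.
- *A PET-positive node left behind after a negative dissection is confirmed by the PSA fall from prostatectomy.* Section B) says "follow-up using imaging as described above will be performed", which points to imaging, and that pathway is worded for suspected recurrence.
- *Prostate and nodes are normally treated together.* The modality list in 1.1.8.1 categorises questionnaire answers and does not show this. How often it happens is unknown.
- *The regional PPV as a whole no longer measures accuracy, or nodal PPV is wholly independent of the truth.* Only regions on this route are affected, and for nodes the enlargement condition and the shrinkage route keep some link to true status.

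The false-positive direction is also partly protected: bone is limited to curative-intent treatment, a bone lesion with an imaging correlate is still true positive, and so is a node that shrinks.

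**Conclusion.** The concern holds for regions classified by the branch for targeted treatment without systemic treatment. There the stated rules let one PSA result decide lesion status. When an in-place primary is treated in the same course, they can label a benign node or distant focus true positive. This produces wrong labels when the rule is followed as written. The undefined term and the undated PSA value add to it.

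The size rests wholly on assumed inputs. If PSA falls in 95% of patients regardless of lesion status, the PPV on this route is 0.95 for bone lesions without an imaging correlate, whatever the truth, and about 0.86 to 0.93 for nodes on the PSA route. The bias in overall regional PPV depends on how many regions use the route, which the documents do not give. For a true value of 0.50 under case 2, it is about +3 points at a 10% share and +16 at 50%. For a true value of 0.90 it is about −2 and −8 points, so even the direction is not fixed. The primary endpoint is not affected. The rules should be changed before PPV is analysed.

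**What to change.** In section 1.1.8.4, 2) A), for nodal, visceral, bone and prostate lesions:

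1. Define targeted treatment as treatment directed at the lesion being classified.
2. Let the PSA criterion, in both the true-positive and false-positive direction, classify a lesion only when its region is the only PET-positive region and no prostate primary outside that region is treated or removed in the same course. Otherwise use pathology or that lesion's own imaging change; failing both, call it unevaluable.
3. Apply the 3-12 month window to the PSA value.
4. In section 1.1.9.5, report how many regions were classified by PSA alone, and report PPV by type of reference standard.

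The cost is protocol wording, fewer evaluable nodal and bone regions at initial staging, and a wider Wilson interval. The loss cannot be sized from the documents. The change concerns outcome classification only and leaves patient care as it is.
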